15.10 Amendment 4 Rationale and Purposes

Rationale for Amendment 4

The purpose of this amendment is to provide information relevant to allowing patients to take study drug at home. Following agreement between the investigator and the sponsor, eligible patients may take study drug at home as directed.

An additional purpose of this amendment is to clarify male contraceptive requirements following the last dose of MLN9708. Previously, the protocol indicated that 30 days was a sufficient period of time for males to use effective methods of contraception. Considering spermatogenesis is 90 days and the half life of MLN9708, the sponsor advises male patients to practice effective barrier contraception or abstinence during the entire study treatment period and through 4 months after the last dose of study drug.

This amendment also provides additional revisions and corrections made to clarify the initial intent of sections as detailed below.

Purposes:

- Provide information relevant to allowing eligible patients to take study drug at home as directed
- Update male contraceptive requirements
- Clarify pharmacokinetic and pharmacodynamic sampling language
- CCI
[REDACTED]
- Update the anticipated duration of study based upon current patient accrual data
- Clarify the starting dose level
- Revise planned Dose Level 3 from 5.2 mg to 5.5 mg
- Add information to the clinical experience summary regarding a patient in Study C16001 who received a dose of MLN9708 higher than was planned per protocol
- Add prophylaxis against risk of infection to the management of clinical events recommendations
- Clarify that a bone marrow aspirate and biopsy may be repeated at the discretion of the investigator as clinically indicated, but is not required during the follow-up period
- Distinguish between investigational (ie, MLN9708) and noninvestigational (ie, dexamethasone) medicinal agents
- Update reference to the Millennium clinician (previously referred to as medical monitor)
- Correct typographical errors, punctuation, grammar, and formatting

15.11 Amendment 5 Rationale and Purposes

Rationale for Amendment 5

This amendment allows for the following: a longer follow-up period for overall survival, an extension for a rollover study should one become available, and flexibility in laboratory evaluations as per standard of care.

Purposes for Amendment 5

The purposes of this amendment are to:

- Update the cover page with current signatories
- Update the duration of the study and overall survival time point
- Update the hematology and chemistry laboratory evaluation schedule
- Update the SAE reporting contact information
- Update the product complaint reporting contact information
- Correct typographical errors, punctuation, grammar, and formatting

15.12 Amendment 6 Detailed Summary of Changes

THE PRIMARY SECTION(S) OF THE PROTOCOL AFFECTED BY THE CHANGES IN AMENDMENT 6 ARE INDICATED. THE CORRESPONDING TEXT HAS BEEN REVISED THROUGHOUT THE PROTOCOL.

Purpose: Update the cover page with current signatories.

The primary change occurs on the cover page:

Formerly ~~Chair~~, Clinical Review Board (or designee)
read:

~~Vice President~~, Oncology Clinical Research (or designee)

Now
reads:

PPD

Purpose: Update the duration of the study and overall survival time point.

The primary change occurs in Section 4.3, Duration of Study:

Formerly It is anticipated that this study will last for approximately 48 months. The
read: duration of follow-up for overall survival will be 2 years after the last patient
enters the study.

Now It is anticipated that this study will last for approximately 84 months. The
reads: duration of follow-up for overall survival will be 60 months after the last
patient enters the study. **Treatment may be continued in this study or in a**
MLN9708 rollover study, if and when such a study is made available,
upon request by the investigator and agreement by the project clinician.

Sections that also contain this change are:

- **PROTOCOL SUMMARY**
- **Section 7.5.17, Follow-Up Assessments (PFS and OS)**

Purpose: Update the hematology and chemistry laboratory evaluation schedule.

The primary change occurs in Section 7.5.10, Clinical Laboratory Evaluations:

Added text: **After 24 cycles on treatment, hematology and chemistry laboratory evaluations may be done to monitor the patient according to standard clinical practice per the treating physician.**

The Schedule of Events also contains this change.

Purpose: Update the SAE reporting contact information.

The primary change occurs in Section 10.2, Procedures for Recording and Reporting Adverse Events and Serious Adverse Events:

Formerly read:

SAE Reporting Contact Information*

~~PPDI Pharmacovigilance (US and Canada)~~
~~24-hour helpline: [contact]~~
~~[contact]~~

~~PPDI Pharmacovigilance (Central and South America)~~

~~24-hour helpline: [contact]~~
~~[contact]~~

~~PPDI Pharmacovigilance (All other countries)~~

~~24-hour helpline: [name]~~
~~[contact]~~

Now reads:

SAE Reporting Contact Information*

CCI

Section 11.11, Product Complaints, also contains this change.

Purpose: Update the product complaint reporting contact information.

The primary change occurs in Section 11.11, Product Complaints:

06 NOV 2012

PPD

MLN9708
Study C16007 Statistical Analysis Plan

LIST OF ABBREVIATIONS AND DEFINITIONS OF TERMS

Abbreviation	Term
AE	adverse event
ALT	alanine aminotransferase
ANC	absolute neutrophil count
AST	aspartate aminotransferase
AUC	area under the concentration versus time curve
AUC _{tau}	area under the concentration-time curve, time 0 to end of dosing interval, estimated using the linear-log trapezoidal method
AUE	area under the effect versus time curve
BLQ	below limit of quantification
CL	clearance
C _{max}	maximum concentration
CSR	clinical study report
C _{trough}	predose concentration
CR	complete response
CRF	case report form
CV	coefficient of variation
CYP	cytochrome P ₄₅₀
dFLC	serum differential free light chain concentration; difference between amyloid forming and non amyloid forming FLC
DLT	dose-limiting toxicity
DNA	deoxyribonucleic acid
ECG	electrocardiogram
ECOG	Eastern Cooperative Oncology Group
EORTC-QLQ-C30	European Organisation for Research and Treatment of Cancer Quality of Life Questionnaire-Core 30
EOS	end of study
EOT	end of treatment visit
E _{max}	maximum observed inhibition value
FLC	free light chain
Ht	height
Hr	hour
INR	international normalized ratio
IV	intravenous; intravenously
λ _z	terminal disposition rate constant
LLOQ	lower limit of quantification
MedDRA	Medical Dictionary for Regulatory Activities
Millennium	Millennium Pharmaceuticals, Inc., and its affiliates
MLN2238	the complete hydrolysis product of MLN9708 to the boronic acid
MTD	maximum tolerated dose
NC	no change
NCI CTCAE	National Cancer Institute Common Terminology Criteria for Adverse Events
ORR	overall response rate
PD	progressive disease (disease progression)
PK	pharmacokinetic(s)

MLN9708
Study C16007 Statistical Analysis Plan

Abbreviation	Term
PR	partial response
PT	prothrombin time
PTT	partial thromboplastin time
QTc	rate-corrected QT interval (millisecond) of electrocardiograph
SAE	serious adverse event
SAP	statistical analysis plan
SD	stable disease
$t_{1/2}$	terminal disposition half-life
TE _{max}	time of occurrence of E _{max}
US	United States
VGPR	very good partial response
WBC	white blood cell
WHO	World Health Organization
Wt	weight

TABLE OF CONTENTS

1. INTRODUCTION	6
1.1 Study Design.....	6
1.2 Study Objectives.....	7
1.2.1 Primary Objective	7
1.2.2 Secondary Objectives	7
1.2.3 Exploratory Objectives	7
2. POPULATIONS FOR ANALYSIS	8
2.1 Safety Population and Enrolled Patients	8
2.2 DLT-Evaluable Population.....	8

1. INTRODUCTION

In general, the purpose of the statistical analysis plan (SAP) is to provide a framework that addresses the protocol objectives in a statistically rigorous fashion, with minimized bias or analytical deficiencies. Specifically, this plan has the following purpose:

To prospectively (a priori) outline the types of analyses and data presentations that will address the study objectives outlined in the protocol, and to explain in detail how the data will be handled and analyzed, adhering to commonly accepted standards and practices of biostatistical analysis in the pharmaceutical industry.

1.1 Study Design

This is an open-label, multicenter, phase 1, dose-escalation study of MLN9708 in adult patients with previously treated systemic light-chain (AL) amyloidosis. A 3 + 3 dose-escalation scheme will be implemented. Patients will receive escalating doses of MLN9708 orally (PO) on Days 1, 8, and 15 in a 28-day cycle in the absence of disease progression (PD) or unacceptable toxicity. If there is no hematologic response (complete response [CR], very good partial response [VGPR], or partial response [PR]) after completion of 3 cycles of single-agent MLN9708, dexamethasone will be added on Days 1 to 4 of every cycle (Days 1-4 every 28 days) beginning with Cycle 4. The patient's response status will be reassessed after 3 additional cycles; if there is no hematologic response at that time, the patient will be removed from treatment and followed for survival.

Once the maximum tolerated dose (MTD)/recommended phase 2 dose (RP2D) has been established, 2 expansion cohorts of patients with relapsed or refractory amyloidosis, including approximately 10 proteasome inhibitor-naïve patients and approximately 16 proteasome inhibitor-exposed patients, will be treated at the MTD/RP2D to more fully characterize the safety, tolerability, and efficacy of MLN9708, quality of life (QOL), and the pharmacokinetics (PK) and pharmacodynamics of MLN9708 in this patient population.

1.2 Study Objectives

1.2.1 Primary Objective

[figure not shown]
- To determine the safety, tolerability, and MTD of PO MLN9708 administered weekly in patients with previously treated relapsed or refractory AL amyloidosis
- To determine the RP2D of PO MLN9708 administered weekly

1.2.2 Secondary Objectives

- To characterize the plasma PK and whole blood pharmacodynamic effect of MLN9708 in this patient population
- To assess the rate of organ response and organ improvement according to standardized criteria
- To assess overall hematologic response rate (CR, VGPR, and PR)
- To assess time to hematologic and organ response
- To assess duration of hematologic and organ response
- To determine time to hematologic and organ disease progression
- To assess progression-free survival (PFS)
- To assess overall survival including 1-year survival rate

1.2.3 Exploratory Objectives

CCI

2. POPULATIONS FOR ANALYSIS

2.1 Safety Population and Enrolled Patients

The Safety population is defined as patients who receive at least 1 dose of MLN9708. The Safety population will be used for all safety analyses. In this study, the enrolled patients are the patients who received at least 1 dose of MLN9708.

2.2 DLT-Evaluable Population

The Dose-Limiting Toxicity (DLT)–Evaluable population is defined as patients who receive all Cycle-1 doses of MLN9708 or experience a DLT in Cycle 1 of the dose-escalation phase. The DLT-evaluable population will be used to determine the MTD.

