The RP2D estimation will be established following evaluation of the available data which will include, but is not limited to, toxicity characterization (Grade 3/4 AEs, SAEs, all grades peripheral neuropathy, and treatment discontinuation) with efficacy (hematologic and organ responses) also taken into consideration. The RP2D will require first cycle DLTs in not more than 0 in 3 or 1 in 6 DLT-evaluable patients enrolled in a single cohort. For the purpose of the RP2D estimation, Cycle 1 data from 6 evaluable patients will be used in addition to the available clinical data supporting tolerance over multiple treatment cycles. AEs that meet DLT criteria in Cycle 2 and beyond will not necessarily influence dose-escalation, but will be considered when determining the RP2D. Toxicities leading to dose modification in Cycle 2 and beyond will not necessarily influence dose-escalation, but will be considered when determining the RP2D.

Once the MTD/RP2D has been established, 2 expansion cohorts of patients with relapsed or refractory amyloidosis, including approximately 10 proteasome inhibitor-naïve patients and approximately 16 proteasome inhibitor-exposed patients, will be treated at the MTD/RP2D to more fully characterize the safety, tolerability, and efficacy of MLN9708, and the PK and pharmacodynamics of MLN9708 in this patient population. As many as 30 patients will be enrolled in the dose-escalation portion of the study, and as many as 20 additional patients (26 in total, including 6 patients from the dose-escalation portion) will be enrolled in the expansion cohorts.

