8.1.3 Populations for Analysis

The populations used for analysis will include the following:

Safety Population: Patients who receive at least 1 dose of MLN9708. The safety population will be used for safety analyses.

DLT-evaluable Population: Patients who receive all Cycle 1 doses of MLN9708 or experience a DLT in Cycle 1. The DLT-evaluable population will be used to determine the MTD.

Organ Response-Evaluable Population: The organ response-evaluable population is defined

as patients who receive at least 1 cycle of MLN9708, have amyloid involvement of at least kidney or heart at baseline, and at least 1 post-baseline organ response assessment.

Hematologic Response-Evaluable Population: The hematologic response-evaluable population is defined as patients who receive at least 1 cycle of MLN9708, have measurable disease at baseline, and at least 1 post-baseline hematologic response assessment.

Plasma PK Analysis Population: Patients who:

- a. Receive full doses of MLN9708 during Cycle 1 without dose reduction or interruptions through the completion of PK sampling
- b. Do not receive any excluded concomitant medications
- c. Have sufficient plasma MLN2238 concentration-time data to permit reliable estimation of plasma PK parameters

Pharmacodynamic Analysis Population: Patients who:

- a. Receive full doses of MLN9708 during Cycle 1 without dose reduction or interruptions
- b. Do not receive any excluded concomitant medications through the completion of pharmacodynamic sampling
- c. Have sufficient whole blood 20S proteasome inhibition-time data to permit reliable estimation of pharmacodynamic parameters

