8.1.8 Safety Analysis

Summary tabulations will be presented that will display the number of observations, mean, standard deviation, median, minimum, and maximum for continuous variables, and the number and percent per category for categorical data.

The incidence of DLT may be tabulated for each dose group. In addition, to assess the relationship between toxicities and MLN9708 dose, the preferred term of individual toxicities may be summarized by their frequency and intensity for each dose group. The DLT-evaluable population will be used for the analysis of DLT. DLT will also be listed for each dose group.

Safety will also be evaluated by the incidence of treatment emergent AEs, severity and type of AEs, and by changes from baseline in the patient's vital signs, weight, and clinical laboratory results using the population evaluable for safety. Exposure to study drug and reasons for discontinuation will be tabulated.

Treatment-emergent events will be tabulated. Treatment emergent is defined as any AE that occurs after administration of the first dose of study drug and up through 30 days after the last dose of study medication, any event that is considered drug related regardless of the start date of the event, or any event that is present at baseline but worsens in severity after baseline or is subsequently considered drug related by the investigator. AEs will be

tabulated according to the Medical Dictionary for Regulatory Activities (MedDRA) by system organ class, high-level terms, and preferred terms and will include the following categories:

- Treatment-emergent AEs
- Drug-related treatment-emergent AEs
- Grade 3 or higher treatment-emergent AEs
- Grade 3 or higher drug-related treatment-emergent AEs
- Treatment-emergent AEs resulting in study drug reduction
- Treatment-emergent AEs resulting in study drug discontinuation
- SAEs

The most commonly reported treatment-emergent AEs (ie, those events reported by $\geq 10\%$ of all patients) will be tabulated by high level term and preferred term.

Descriptive statistics for the actual values and/or change from baseline of clinical laboratory parameters will be presented for all scheduled measurements over time. Mean laboratory values over time will be plotted for key laboratory parameters.

Descriptive statistics for the actual values and changes from baseline of vital signs, weight, and ECOG scores will be tabulated by scheduled time point.

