5.10.1.5 Dose Limiting Toxicities

A by-patient listing of DLTs that occur during Cycle 1 of treatment will be presented by dose level for all patients enrolled during the dose-escalation portion of this study. Patients will be grouped by the dose level to which they were originally assigned, including those who receive subsequent treatment at a lower dose level.

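### The SAP confines DLT evaluation and listing to dose escalation without declaring the change, so Cycle 1 DLTs in up to 20 expansion patients would be neither listed nor counted as DLTs

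*SAP*

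**What the plan says.** Protocol 8.1.3 defines the DLT-evaluable population as "Patients who receive all Cycle 1 doses of MLN9708 or experience a DLT in Cycle 1", with no mention of study phase. It gives the purpose: "The DLT-evaluable population will be used to determine the MTD". Protocol 8.1.8 adds a second use: "The DLT-evaluable population will be used for the analysis of DLT". The same section leaves tabulation of DLT incidence optional, but commits without condition to listing DLTs by dose group.

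SAP 2.2 defines the population as patients who take every Cycle 1 dose or "experience a DLT in Cycle 1 of the dose-escalation phase", again for determining the MTD. SAP 5.10.1.5 plans one DLT output, a by-patient listing of Cycle 1 events by dose level "for all patients enrolled during the dose-escalation portion of this study". No DLT rate is planned. SAP Section 6, which records departures from the protocol, covers the PK and pharmacodynamic populations and the vital-organ terminology. It does not mention the DLT population.

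On the dose decision, protocol 6.4 sets the limit: "The RP2D will require first cycle DLTs in not more than 0 in 3 or 1 in 6 DLT-evaluable patients enrolled in a single cohort". It also states the evidence base: "For the purpose of the RP2D estimation, Cycle 1 data from 6 evaluable patients will be used in addition to the available clinical data". The expansion cohorts open only after the MTD/RP2D has been set.

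**The concern.** The expansion exists partly to characterise safety and tolerability at the chosen dose more fully. Under the SAP, an expansion patient who meets a DLT criterion in Cycle 1 appears in no DLT listing and no DLT count, although the protocol's definition and its listing commitment carry no phase limit.

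The planned adverse event tables do not fill this gap. SAP 5.10.1.1 tabulates events by term and grade, with no restriction to Cycle 1. The DLT criteria in protocol 6.3.1 depend on more than term and grade: duration of Grade 4 cytopenias, a platelet count below 10,000/mm³, Grade 2 neuropathy with pain, and a delay of more than 2 weeks in starting Cycle 2. They also exempt some Grade 3 events. A Cycle 1 DLT count cannot be recovered from tables by term and grade.

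The SAP sentence is also ambiguous. The phase restriction may apply to both routes into the population or only to the second (having a DLT). On the narrower reading, an expansion patient who takes every Cycle 1 dose is DLT-evaluable, while one who misses a dose because of a DLT is not.

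**Working it through.** **1. Patient numbers (protocol 4.1, 6.4 and 8.1.1).** Expansion cohorts: 10 + 16 = 26. From escalation: 6. Newly enrolled in expansion: 26 − 6 = 20. Study total: 30 + 20 = 50. All agree with the stated figures. The documents state no precision for a DLT rate, so there is no such figure to reproduce.

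**2. The texts side by side.**

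| Item | Protocol | SAP |
|---|---|---|
| DLT-evaluable population | No phase limit (8.1.3) | Escalation phase named (2.2) |
| DLT listing | By dose group (8.1.8) | Escalation patients only (5.10.1.5) |
| DLT incidence | Optional (8.1.8) | None planned |
| Change declared | – | No (Section 6) |

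**3. Precision of a Cycle 1 DLT rate.** For x DLTs in n patients, the two-sided 95% Clopper-Pearson limits are: lower = 0.025 quantile of Beta(x, n − x + 1), upper = 0.975 quantile of Beta(x + 1, n − x). When x = 0 the lower limit is 0. The DLT counts are assumptions, apart from 0/6 and 1/6, which are the six-patient results compatible with the protocol 6.4 limit.

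| x/n | Rate | Exact 95% interval |
|---|---|---|
| 0/6 | 0% | 0 to 45.9% |
| 1/6 | 16.7% | 0.4 to 64.1% |
| 0/26 | 0% | 0 to 13.2% |
| 4/26 | 15.4% | 4.4 to 34.9% |
| 4/22 (if only 22 of 26 are evaluable) | 18.2% | 5.2 to 40.3% |

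At a rate near 16%, the width falls from about 64 to about 30 percentage points.

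**4. How much the escalation result leaves open.** With true DLT rate p and q = 1 − p, a dose passes the 3 + 3 rule with probability q³ + 3pq² × q³.
- p = 0.30: 0.343 + 0.441 × 0.343 = 0.494.
- p = 0.40: 0.216 + 0.432 × 0.216 = 0.309.

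If six patients are always treated, the chance of at most 1 DLT is q⁶ + 6pq⁵: 0.420 at p = 0.30 and 0.233 at p = 0.40. Passing is therefore weak evidence that the rate is low. This is a property of the 3 + 3 design, not of the SAP wording, but it shows why DLT data from the expansion are worth reporting.

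**5. The ambiguous wording, if a rate were computed from it.** Assume 1 DLT in 6 during escalation and 4 DLTs among 20 expansion patients, each causing a missed dose. On the narrower reading those 4 leave the population: 1/(26 − 4) = 1/22 = 4.5%. Under the protocol definition, with all other patients evaluable, the rate is (1 + 4)/26 = 19.2%.

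**The case against.** The strongest reply is that the SAP phrase only clarifies. Both documents tie the population to determining the MTD, the expansion starts after that decision, and protocol 7.9 applies DLT evaluability to replacement in the escalation part. Protocol 8.1.5 distinguishes dose levels from expansion cohorts, so the dose groups in 8.1.8 might be read as escalation groups. This has weight for the MTD. It does not settle the matter, because 8.1.8 also assigns the population to DLT analysis in general, and a narrowing of that use belongs in SAP Section 6.

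Three stronger readings are tempting, and the documents do not support them:
- **The SAP makes the RP2D, or toxicity at that dose in general, rest on 6 patients.** The six-patient basis comes from protocol 6.4 and would be the same under either definition. Adverse events, SAEs and laboratory data are analysed in the Safety population (SAP 2.1 and 5.10), and SAP 5.4.4 foresees summaries of all patients at the MTD.
- **A primary endpoint goes unreported.** Protocol 3.1 names adverse events, SAEs, laboratory values, neurotoxicity grading and the MTD/RP2D. A DLT rate is not among them, and neither document promises an interval for one.
- **A planned estimate is biased.** The SAP plans no DLT rate, so the contrast in step 5 is hypothetical. As planned, the ambiguity reaches only the count of DLT-evaluable patients in the SAP 5.5 disposition table.

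It is also fair to say that the table proposed below goes beyond the protocol's firm commitments, and that some DLT criteria need judgement rather than programming.

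**Conclusion.** The point holds as an undeclared narrowing with a limited but real loss. The SAP drops a protocol commitment to analyse and list DLTs without a phase limit, so Cycle 1 DLTs in up to 20 expansion patients at the MTD/RP2D would be neither listed nor counted as DLTs. The MTD/RP2D decision does not change, and general toxicity reporting at that dose is intact.

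The gain from correcting it is precision on one descriptive measure: 0.4% to 64% for 1/6, against 4% to 35% for an assumed 4/26. That comparison assumes full expansion enrolment and that all 26 are DLT-evaluable. Twenty-six is a planned maximum, since SAP 5.1 lets the sponsor stop expansion enrolment at any time. It also assumes that DLT status can be established in expansion patients. Protocol 6.5.1 makes this plausible: it bars Cycle 1 dose modification unless a DLT is documented, with no phase limit.

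**What to change.** - **SAP 2.2:** restore the protocol 8.1.3 definition by removing the escalation-phase wording. Name the escalation patients as the subset used to determine the MTD, and record that distinction in SAP Section 6.
- **SAP 5.10.1.5:** extend the by-patient listing of Cycle 1 DLTs to all patients treated at each dose level, marking escalation and expansion patients.
- **New descriptive table:** Cycle 1 DLT incidence with an exact 95% interval for all DLT-evaluable patients at the MTD/RP2D (at most about 26). Show the escalation and expansion rows beside the pooled one, because the escalation patients at that dose are there after passing the dose rule.

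The cost is one table and one extended listing. Investigators would need to apply the less mechanical criteria in expansion patients, such as relatedness, clinically significant bleeding and adequacy of anti-emetic prophylaxis. The resulting rate may be less favourable than the one in the escalation cohort.
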